## 6 ANALYSIS POPULATIONS

The following analysis populations are defined for the main and fibrate expansion cohorts.

**Table 5. Analysis Population**

Population	Definition
Screened Analysis Set	All subjects who signed informed consent and have undergone screening.
Randomized Analysis Set	All subjects in screened analysis set who are assigned a randomization number in the study.
Full Analysis Set	All randomized subjects who received at least 1 dose of investigational product, have a baseline, and at least 1 post-baseline TG measurement not including EOS visit.
Safety Analysis Set	All subjects who received at least 1 dose of investigational product.
Trough PK Analysis Set	All subjects in the Safety Analysis Set, who have pre-dose and at least 1 post-dose trough PK measurements.
Intensive PK Analysis Set	All subjects in the Safety Analysis Set, who opted to participate in the Intensive PK scheme, and have at least 1 on-study PK measurement.
MRI-PDFF Analysis Set	All subjects in the Full Analysis Set who have baseline and a follow up MRI-PDFF assessments.

All primary, secondary, and exploratory efficacy endpoints will be assessed for all subjects in the Full Analysis Set. All safety assessments will be displayed and analyzed for all subjects in the Safety Analysis Set. Intensive PK endpoints will be displayed and analyzed for all subjects with applicable data in the Intensive PK Analysis Set.

[figure not shown]
## 6.1 HANDLING OF MISSING AND INCOMPLETE DATA

[figure not shown]
### 6.1.1 Missing Dates

For the missing or partially missing dates for the adverse event, prior/concomitant medication and procedures, the missing date will be imputed following the rules below.

Protocol No: BIO89-100-221 V3.0  
Version: 1.0

Statistical Analysis Plan  
Date: 03June2022

### 6.1.2 Missing data for Efficacy Endpoints

Missing data handling will be explored as sensitivity analysis if there is more than 10% missing data for the primary efficacy endpoint. The details are described in [Section 7.5](#).

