## 9.2. Sample Size Determination

The effect of BIO89-100 on the percentage change from baseline in TG is estimated based on prior clinical studies evaluating BIO89-100 and other TG lowering agents:

Based on these results, it is estimated that the SD of the percent change in TG at Week 8 is  $\sim$ 40%. With 18 subjects in the placebo group and each BIO89-100 dose group, there would be at least 86% power to detect a 45% difference in TG between each BIO89-100 dose group and placebo at the 2-sided alpha level of 0.05, assuming 50% reduction in BIO89-100 dose group and 5% in the placebo group.

Fatty liver has been shown to be significantly associated with moderately severe or severe acute pancreatitis (Yoon, et al. 2017). Hence, another focus of this study is to assess the BIO89-100 effect on reducing liver fat as assessed by MRI-PDFF in the SHTG population, with or without concurrent stable fibrate therapy. In Study BIO89-100-002 (Part 1), BIO89-100 (27 mg QW) reduced liver fat as assessed by MRI-PDFF up to 60%. In the main cohort not on concomitant fibrate therapy, a sample size of ~30 subjects (e.g., ~33% of the main cohort total sample size, ~6 placebo vs ~24 pooled BIO89-100) is estimated to provide ~89% power to detect a difference of at least 50% mean percentage reduction in MRI-PDFF at Week 8 compared to placebo, using a significance level of 0.05 (2-sided). These calculations are based on an assumption that the percentage change from baseline in MRI-PDFF is normally distributed with a standard deviation of no greater than 30%, as estimated from data in Study BIO89-100-002. In the fibrate expansion cohort, assuming a difference of 50% mean percentage reduction in MRI-PDFF at Week 8

compared to placebo, a standard deviation of no greater than 30% under normal assumption, and a significance level of 0.05 (2-sided), the planned sample size of 18 subjects per group will have >99% power to detect such a mean difference.

This sample size assessment incorporates approximately 10% of subjects lost to follow-up.

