### 3.5 SAMPLE SIZE CONSIDERATIONS

The effect of BIO89-100 on the percentage change from baseline in TG is estimated based on prior clinical studies evaluating BIO89-100 and other triglyceride lowering agents. [REDACTED]

[REDACTED]

[REDACTED]

[REDACTED]

[REDACTED]

[REDACTED]

[REDACTED]

[REDACTED]

[REDACTED]

Based on these results, it is estimated that the SD of the percent change in TG at Week 8 is approximately 40%. With 18 subjects in the placebo group and each BIO89-100 active treatment group, there would be at least 86% power to detect a 45% difference in TG between each BIO89-100 active treatment group and placebo at the 2-sided alpha level of 0.05, assuming 50% reduction in BIO89-100 dose group and 5% in the placebo group. This sample size assessment incorporates approximately 10% of subjects will be lost to follow-up.

Approximately 90 subjects are planned to be enrolled in the main cohort, with 18 subjects in each of the BIO89-100 active treatment groups (9 mg QW, 18 mg QW, 27 mg QW, or 36 mg Q2W) and in the placebo group. The study aims to enroll ~33% of subjects (~30 subjects total) in the main cohort with a baseline MRI-PDFF  $\geq$  6%. Approximately 36 subjects are planned to be enrolled in the fibrate expansion cohort (18 in each treatment group) with all subjects having baseline MRI-PDF  $\geq$  6%. Subjects who terminate early in either cohort may be replaced at Sponsor's discretion.

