## 7 STATISTICAL METHODS OF ANALYSES

### 7.1 GENERAL CONSIDERATIONS

The statistical analysis for this study will be performed by combining the main cohort and the fibrate extension cohort. A single database lock will be implemented.

All the tables and figures will be based on the pooled data from both cohorts, unless otherwise specified. One set of listings will be generated for the whole study.

In general, summaries and analyses will be presented by dose/treatment group. Descriptive statistics will be presented for demographics and baseline characteristics, safety endpoints, and PK and PD parameters. Continuous variables will be summarized by number of subjects and mean, SD/standard error, median, minimum, and maximum values. Minimum

---

and maximum will be presented to the same number of decimal places as reported/collected. One additional decimal place will be presented for mean and median. Two additional decimal places will be presented for SD up to a max of three decimal places.

Categorical variables will be summarized by number and percentage of subjects. Percentage will be presented to one decimal place. The number of missing values will be presented as a separate category with no percentage, but only if 1 or more subjects are missing data for the summary. Otherwise, all categories will be presented (even if no subjects are counted in the category). Counts of zero in any category will be presented without percentage.

All statistical tests will be 2-sided and tested at a statistically significant level of 0.05 without adjustment for multiplicity. Confidence intervals will be 2-sided 95%, unless stated otherwise. Two-sided p-values will be presented with four decimal places and values less than 0.0001 will be presented as <.0001.

Both reported units (CN) and SI units will be presented in listings.

Both CN and SI units will be used in lipid panel (TG and other lipids) tables and figures.

For the rest, only CN units will be used for tables and figures, unless otherwise specified. Insulin will be presented with conventional unit of  $\mu$ IU/mL;

The listings will only present non-imputed data.

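### The missing-data sensitivity analysis depends on a 10% trigger with no stated denominator and no per-arm rule, so heavy dropout in one 18-subject arm could leave it unrun.

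*SAP*

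**What the plan says.** SAP Section 6.1.2 states: "Missing data handling will be explored as sensitivity analysis if there is more than 10% missing data for the primary efficacy endpoint". It refers to Section 7.5 for details. The readable text of 7.5 and 7.5.1 gives neither a denominator for the 10% nor an imputation method, but part of 7.5.1 is redacted.

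Four other provisions bear on this:

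- **Arm sizes.** SAP Section 3.5: "Approximately 90 subjects are planned to be enrolled in the main cohort, with 18 subjects in each of the BIO89-100 active treatment groups" and in the placebo group. Also: "Approximately 36 subjects are planned to be enrolled in the fibrate expansion cohort (18 in each treatment group"). That is 126 planned in total. Section 7.1 adds: "The statistical analysis for this study will be performed by combining the main cohort and the fibrate extension cohort".
- **Primary analysis.** SAP Section 7.5.1 uses a mixed model for repeated measures (MMRM) with all planned visits up to Week 8. Protocol Section 9.4.2 had ANCOVA on observed data as primary, and the MMRM as a sensitivity analysis with no missingness trigger. The SAP supersedes it.
- **Success rule.** SAP Section 7.5 counts the study as positive if any comparison is significant, pooled or single-dose.
- **Planned loss.** SAP Section 3.5: "This sample size assessment incorporates approximately 10% of subjects will be lost to follow-up". Protocol Section 9.2 says the same.

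**The concern.** An MMRM gives a fair Week 8 comparison only if, given the observed visits and covariates, missing values resemble observed ones. A missing-data sensitivity analysis exists to test that. Here it runs only above a threshold, and nothing readable ties the threshold to the arm in which dropout occurs.

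The comparisons are arm by arm. Three of the four active groups are planned at 18 subjects even after the cohorts are pooled, and one significant dose is enough for success. Protocol Section 4.2 says the results will inform Phase 3 dose selection. Dropout concentrated in one dose group is therefore the case that most needs checking. A single overall percentage dilutes it by the size of the other arms, and pooling the fibrate cohort dilutes it further.

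**Working it through.** **Inputs from the documents.** 18 per arm, five arms, N=90 in the main cohort. With the fibrate cohort pooled, placebo 36, 9 mg 18, 18 mg 18, 27 mg 36, 36 mg Q2W 18, so N=126. Difference 45 points, SD about 40, two-sided alpha 0.05, loss about 10% (SAP Section 3.5). Trigger: more than 10% missing (SAP Section 6.1.2). The arm-specific missing rates below are assumptions.

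**1. The plan's own figure.** Two-sample t-test power (noncentral t) at difference 45, SD 40: 16 evaluable per arm (18 × 0.9 = 16.2) gives 86.8%, and 18 per arm gives 90.6%. The stated power of at least 86% is reproduced with about 10% loss per arm.

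**2. What an overall trigger lets through.**
- N=90: 9/90 = 10.0% is not more than 10%, so up to 9 missing does not trigger. Five in one arm and one in each of the other four is 5 + 4 = 9. That arm has 5/18 = 27.8% missing. At the extreme, all nine in one arm is 9/18 = 50%.
- N=126: 12/126 = 9.5% does not trigger; 13/126 = 10.3% does. The same pattern of nine missing is 9/126 = 7.1%.

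**3. Probability that the check is skipped.** One arm of 18 has missing rate p and all others 5%. The total missing is a sum of independent binomials; the check is skipped if the total is at most 9 (N=90) or 12 (N=126).

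| Missing in one arm of 18 | Missing elsewhere | Skipped, N=90 | Skipped, N=126 |
|---|---|---|---|
| 20% | 5% | 0.82 | 0.89 |
| 30% | 5% | 0.59 | 0.72 |
| 40% | 5% | 0.33 | 0.50 |

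For the 30% row, the expected overall rate is (18 × 0.30 + 72 × 0.05)/90 = 10.0% at N=90, and (18 × 0.30 + 108 × 0.05)/126 = 8.6% at N=126.

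**4. Size of a possible bias (illustration).** Suppose 4 of 18 in an active arm are missing, truly revert to placebo level, and the model treats them as continuing responders. The overstatement is 4/18 × 45 = 10 points: 45 estimated against 45 × (1 − 4/18) = 35. This is an upper figure for that scenario.

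**5. How often that much loss goes unflagged by chance.** With uniform 9% loss and N=126, the check is skipped with probability 0.65. Among those untriggered trials, at least one active arm has 4/18 or more missing (8/36 for the 27 mg group) in about 10%, or about 7% of all trials.

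**6. A per-arm reading.** More than 10% of 18 means 2 or more missing. At a true 10% in each of five arms of 18, one arm meets this with probability 0.55, and at least one of the five with 1 − (1 − 0.55)^5 = 0.98.

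**The case against.** **The denominator is not stated.** A per-arm reading would remove the skipping problem. That stands: the result in step 3 holds for the overall reading only. But the text does not settle the matter, and on the per-arm reading the condition is met almost always (step 6) and does no useful work.

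**The trigger equals the planned loss, so running the check is a coin toss.** A reader might infer this, because at exactly 10% missing the trigger fires with probability 0.41 (N=90) or 0.50 (N=126). The documents do not support it. The 10% in SAP Section 3.5 is loss to follow-up, while the trigger counts missing primary-endpoint data, for which no forecast is given. Several rules lower the latter: one available value suffices for Week 8 (7.5.1), unscheduled and early end-of-treatment visits are mapped to analysis windows (6.2), and subjects without a post-baseline triglyceride value are outside the Full Analysis Set (Section 6). At 5% missing the trigger fires in about 1% of trials.

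**No other check exists.** This cannot be said either. The redacted block in 7.5.1 may hold the method, a per-arm rule or a missing-not-at-random analysis. The trigger sentence is not redacted, however, and it governs whether the 6.1.2 analysis runs.

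**Dropout could produce a false positive.** This is not shown. In the step 4 illustration 35 points remain; with SD 40 and 18 against 36 subjects, t-test power is still about 84%.

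**Proportionality.** This is an 8-week Phase 2 study, the MMRM uses partial data from dropouts, and SAP Section 7.2 summarizes discontinuations by reason. Making such a check conditional is a common choice. This limits the severity, but it does not make an overall trigger suited to arm-level comparisons.

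**Conclusion.** The point holds as a flaw in a stated rule and is a cheap improvement. The trigger has no defined denominator and no per-arm rule. Read as an overall rate, it would leave the check unrun with probability about 0.59 to 0.72 when one 18-subject arm has 30% missing and the others 5%.

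Those rates are assumed. N=126 is the planned total; SAP Section 5.5 reports low fibrate-cohort enrolment, so the actual N probably lies between 90 and 126 if the main cohort reached its target.

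The overstatement of up to about 10 points is illustrative. It needs 4 of 18 missing in an active arm, full reversion to placebo level, and an estimand that counts that reversion. Under uniform 9% loss and N=126, that fraction missing in an active arm arises in about 10% of untriggered trials, so it should not be presented as the usual outcome.

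**What to change.** In SAP Section 6.1.2, delete the 10% condition and always run the sensitivity analysis already planned. Report the number and percentage with a missing primary endpoint by treatment arm, and name the denominator. If the redacted method rests only on missing at random, make one version missing-not-at-random, for example placebo-based imputation for active-arm dropouts.

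The cost is a little extra programming and one more result to report and interpret. No new data are needed.

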## 6.2 ANALYSIS VISIT WINDOWS

In general, all screening visits will be combined as Screening Analysis Visit. Scheduled visits from randomization (except for EOT visit for early terminated subjects) through [REDACTED]/Week 8 will be used as analysis visit for descriptive analysis tables and listings.

Unscheduled visits will be mapped according to the analysis visit window below. If a scheduled visit is missing, the unscheduled visit that is closest to the target study day may be used for analysis purpose.

For early terminated subjects, EOT visits will be remapped to scheduled visit week using the actual study day and analysis window. EOS visits will be analyzed separately.

Both nominal visits and analysis visits will be displayed in the listing.

The visit schedules and window are shown below.

**Table 6. Analysis visit window**

Nominal Visit/Time point	Analysis Visit Label	Target Study Day a	Analysis Window a

### 6.3 SOFTWARE

All data processing, summarization and analyses will be performed using SAS Version 9.4 or later of the SAS® statistical software package.

## 7 STATISTICAL METHODS OF ANALYSES

### 7.1 GENERAL CONSIDERATIONS

The statistical analysis for this study will be performed by combining the main cohort and the fibrate extension cohort. A single database lock will be implemented.

All the tables and figures will be based on the pooled data from both cohorts, unless otherwise specified. One set of listings will be generated for the whole study.

In general, summaries and analyses will be presented by dose/treatment group. Descriptive statistics will be presented for demographics and baseline characteristics, safety endpoints, and PK and PD parameters. Continuous variables will be summarized by number of subjects and mean, SD/standard error, median, minimum, and maximum values. Minimum

---

and maximum will be presented to the same number of decimal places as reported/collected. One additional decimal place will be presented for mean and median. Two additional decimal places will be presented for SD up to a max of three decimal places.

Categorical variables will be summarized by number and percentage of subjects. Percentage will be presented to one decimal place. The number of missing values will be presented as a separate category with no percentage, but only if 1 or more subjects are missing data for the summary. Otherwise, all categories will be presented (even if no subjects are counted in the category). Counts of zero in any category will be presented without percentage.

All statistical tests will be 2-sided and tested at a statistically significant level of 0.05 without adjustment for multiplicity. Confidence intervals will be 2-sided 95%, unless stated otherwise. Two-sided p-values will be presented with four decimal places and values less than 0.0001 will be presented as <.0001.

Both reported units (CN) and SI units will be presented in listings.

Both CN and SI units will be used in lipid panel (TG and other lipids) tables and figures.

For the rest, only CN units will be used for tables and figures, unless otherwise specified. Insulin will be presented with conventional unit of  $\mu$ IU/mL;

The listings will only present non-imputed data.

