#### 4.7 COVARIATES AND SUBGROUPS

- TG  $<750$  mg/dL or  $\geq 750$  mg/dL
- Background lipid medication (Yes, No)
- Type of background lipid medication (use of statin (including combo therapy), use of fibrate therapy, use of prescription fish oil, Ezetimibe, and Bempedoic acid), provided there is sufficient number of subjects in the subgroup
- Type 2 diabetes (Yes, No)
- Age categories (21-<65,  $\geq 65$ ).

- Sex (male, female)
- Baseline weight <median and  $\geq$  median
- Region (US vs EU)
- TG responder at Week 8 (responder, non-responder)
- Use of background insulin medication (Yes/No) for insulin analysis only

Note, if the percentage of subjects within a certain subgroup is less than 33% (i.e., less than 6 of 18 subjects) of the overall cohort, only descriptive analysis will be performed.

More details of the analyses repeated in the above subgroups are described in [Section 7.5.1](#).

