**Table 2. Table Header for Pooled Analysis**

<Description>	Placebo QW	BIO89-100	Total
---------------	------------	-----------	-------

	Pooled	Pooled	
--	--------	--------	--

2. A comparison between individual BIO89-100 dose group and the placebo group.

Each BIO89-100 dose group will be compared with the placebo group. Due to the low number of subjects enrolled in the fibrate cohort, subjects randomized to BIO89-100 in fibrate cohort will be combined with the 27mg QW main cohort as the pooled 27mg QW group. The subjects randomized to placebo in the fibrate cohort will be combined with the placebo group. The table header is shown below (Table 3). The Total group will be presented as appropriate.

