## 7.5 EFFICACY ANALYSIS

The objective for the primary efficacy analyses is to evaluate the effect of BIO89-100 on TG reduction after the 8-week treatment period. The analyses consist of comparisons between the BIO89-100 groups and placebo as below:

1. A pooled BIO89-100 group combining all dose groups will be compared with the placebo to evaluate the overall effectiveness of BIO89-100
2. Individual BIO89-100 dose groups will be compared with the placebo group separately to evaluate the effectiveness of BIO89-100 at a specific dose

The study is considered positive and meeting the primary objective if any of the comparisons above is statistically significant.

All efficacy analysis will be performed using the FAS unless otherwise specified. Analyses comparing the placebo group and the pooled BIO89-100 group will be stratified if the sample size permits. The analyses comparing the placebo and individual dose group will not be stratified due to anticipated small size.

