### 7.5.1 Analysis of Primary Efficacy endpoints

The primary endpoint is the percent change in TG at Week 8 from baseline. The TG value at week 8 is defined as the average of TG values at [REDACTED]

[REDACTED] In case of missing TG value at [REDACTED] the non-missing result will be used as the week 8 TG. The primary efficacy analysis will be performed using a mixed model with repeated measure (MMRM). The model includes the treatment group, baseline TG values, background therapy use, visit, visit and treatment interaction. The model will be fitted using all planned visits up to Week 8.

If the mixed model assumption of the MMRM method is severely violated, the non-parametric van Elteren test stratified by baseline TG level and background lipid therapy will be used to test the treatment difference using the pooled data. The location shift estimate, and Hodges-Lehmann 2-tailed 95% confidence interval will be presented. For the comparison between the individual dose group and the placebo, the unstratified Wilcoxon rank-sum test will be used instead due to the low sample size.

The primary efficacy analysis will be repeated in the subgroups (as noted in [Section 4.7](#)).

[REDACTED]  
[REDACTED]  
[REDACTED]  
[REDACTED]

[REDACTED]  
[REDACTED]  
[REDACTED]

[REDACTED]

[REDACTED]

[REDACTED]

[REDACTED]

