### 7.5.2 Analysis of Secondary Efficacy Endpoints

Full analysis set will be used for all secondary efficacy analyses. The proportion of subjects with TG <500 mg/dL at Week 8 will be summarized by treatment group and analyzed using Cochran Mantel Haenszel (CMH) method stratified by the 2 stratification. Unstratified Chi-square test will be performed for comparisons between the placebo and the individual dose group or if the sample size within a stratum is too small (< 5 subjects). In addition, responder analysis at Week 8 will be performed to ensure the consistency of the results. The following threshold will be used to calculate: the proportion of subjects with TG normalized; with TG reduction by  $\geq 30\%$ ,  $\geq 40\%$ ,  $\geq 50\%$ ,  $\geq 60\%$ ,  $\geq 70\%$ ,  $\geq 80\%$ , and  $\geq 90\%$  from baseline.

Cumulative distribution function of both percentage changes from baseline and changes from baseline for TG at Week 8 by treatment group will be summarized descriptively and graphically.

Percentage change in VLDL-C, LDL-C, non-HDL-C, HDL-C, VLDL-TG, ApoB, hsCRP, fasting plasma glucose, adiponectin, and body weight from baseline to Week 8 will be analyzed similarly as the primary endpoints. For parameters that only have one post-baseline measurement, an ANCOVA model will be performed with treatment and background therapy as factors and baseline value as covariate.

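### Combining the two separately randomised cohorts without a readable cohort term leaves the pooled and the 9, 18 and 36 mg contrasts open to confounding by cohort; the effect is probably small and cheap to remove

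*SAP*

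**What the plan says.** Protocol 6.4 describes two randomisations. The main cohort is allocated equally to 9 mg QW, 18 mg QW, 27 mg QW, 36 mg Q2W or placebo. The fibrate expansion cohort is allocated 1:1 to 27 mg QW or placebo, in subjects on a stable fibrate dose with liver fat of at least 6.0%. Protocol 6.7.1 prohibits fibrates in the main cohort. Protocol 9.4.1 planned a separate analysis for each cohort.

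The SAP, which by its section 1 takes precedence on analysis, changes this. Section 7.1: "The statistical analysis for this study will be performed by combining the main cohort and the fibrate extension cohort". The reason in section 5.5 begins: "Due to the low number of subjects enrolled in the fibrate cohort". Fibrate-cohort active subjects are merged into 27 mg QW, and on placebo it says: "The subjects randomized to placebo in the fibrate cohort will be combined with the placebo group". That one placebo group then serves every dose.

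On the primary model, SAP 7.5.1 says: "The model includes the treatment group, baseline TG values, background therapy use, visit, visit and treatment interaction". The nonparametric fallback for the pooled contrast is stratified by baseline TG and background lipid therapy. For single doses, SAP 7.5 says: "The analyses comparing the placebo and individual dose group will not be stratified due to anticipated small size". On success: "The study is considered positive and meeting the primary objective if any of the comparisons above is statistically significant".

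**The concern.** Within each cohort, randomisation protects the comparison of active with placebo. Once the cohorts are merged, protection remains only where both sides of a contrast contain the same share of fibrate-cohort subjects. That is true for 27 mg against placebo. It is not true for 9, 18 and 36 mg, which contain none of these subjects while their comparator does, nor for the pooled contrast, where the share is lower in active than in placebo.

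Background therapy use does not stand in for cohort. Protocol 1.1 and SAP 3.4 describe it as prescription fish oil and/or statins. SAP 4.7 lists fibrate among the types of background lipid medication ("use of statin (including combo therapy), use of fibrate therapy, use of prescription fish oil"), and no readable text says how fibrate users are coded in the model.

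If TG falls less in the fibrate cohort on the same treatment, 9, 18 and 36 mg look better than they are; if it falls more, they look worse. The 27 mg contrast does not move. Protocol 4.2 says the results are to inform Phase 3 dose selection, so an uneven shift between doses matters more than its size alone suggests.

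**Working it through.** **Inputs from the documents.** 18 per main-cohort arm; SD 40 points; difference 45 points; two-sided 0.05; about 10% loss (Protocol 9.2, SAP 3.5). SAP 3.3 prints four terms in the main-cohort ratio for five groups; the protocol's 1:1:1:1:1 is used here.

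**Assumptions.** The number of fibrate-cohort subjects per arm, f, is not given: 2 and 5 are used for low enrolment. D is not given: 10 and 20 points are used.

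**The plan's own figure.** A two-sample t-test with 16 per arm (18 less 10%), difference 45 and SD 40 has power 86.8%, which reproduces the stated 86%.

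**Bias.** The expected bias is D times the difference in fibrate-cohort share between placebo and active.
- 9, 18 or 36 mg: f/(18+f) - 0. For f = 2, 2/20 = 0.10. For f = 5, 5/23 = 0.22.
- Pooled: f/(18+f) - f/(72+f). For f = 2, 0.100 - 0.027 = 0.07. For f = 5, 0.217 - 0.065 = 0.15.
- 27 mg: f/(18+f) on both sides, so 0.

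| f per arm | D | Bias, pooled | Bias, 9/18/36 mg |
|---|---|---|---|
| 2 | 20 | 1.5 | 2.0 |
| 5 | 10 | 1.5 | 2.2 |
| 5 | 20 | 3.0 | 4.3 |

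**If fibrate users are coded as on background therapy.** With an assumed 30-70% of the main cohort on background therapy, the multipliers at f = 5 fall only to 0.13-0.15 (pooled) and 0.18-0.21 (single dose).

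**False-positive rates.** Least-squares simulation, SD 40, no treatment effect:
- f = 2, D = 20: about 5.1% for the pooled and for each affected single-dose contrast.
- f = 5, D = 10: about 5.2-5.3%.
- f = 5, D = 20: about 6%.
- Chance that at least one of the five comparisons is significant: about 16% with D = 0, because there is no multiplicity adjustment; about 16% at f = 2, D = 20; about 18% at f = 5, D = 20.

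**Why a simple cohort term is not enough for 9, 18 and 36 mg.** Let I be the extra effect of 27 mg in fibrate users. An additive cohort term is estimated from placebo and 27 mg together, so it absorbs I/2 and passes f/(18+f) × I/2 to the other doses: 0.05 I at f = 2 and 0.11 I at f = 5. Comparison with main-cohort placebo carries none of D or I.

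**Standard errors at SD 40.**
- Single dose, merged placebo: 40 × √(1/18 + 1/20) = 13.0, or with 1/23, 12.6. Main-cohort placebo: 40 × √(2/18) = 13.3.
- Pooled, merged: 40 × √(1/74 + 1/20) = 10.08, or 40 × √(1/77 + 1/23) = 9.50. With cohort: 40/√(14.4 + f/2) = 10.19 or 9.73, where 14.4 = 72 × 18/90. Main cohort only: 40/√14.4 = 10.5.

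**The case against.** The strongest reply is that the effect is small. The biases above are 1.5 to 4.3 points, against standard errors of about 10 to 13 and a design difference of 45. The fibrate dose is stable, both cohorts meet the same TG entry criteria, and baseline TG is in the model. The chance of at least one significant result is already about 16% through a separate choice, and cohort adds at most about 2 points. All of this stands and limits the severity.

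Combining the cohorts is also an open, reasoned decision. Low enrolment explains why the fibrate cohort cannot be analysed alone. It does not explain why its placebo subjects should serve as comparator for doses that cohort never received.

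A main-cohort result may also be available. Fibrate use is a subgroup in SAP 4.7, and a table of non-users would be close to a main-cohort analysis. A reader might infer that the 33% rule there would reduce such a table to description. It would not: non-users would be 90 of 100 at f = 5 and 90 of 126 at planned size. Text in SAP 7.5.1 and all of Appendix 2 is redacted and may hold a by-cohort analysis. Such a result would help expose any distortion, but a supportive table would not change the primary comparison.

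**Conclusion.** The point holds as a minor to moderate weakness. In the readable text, the pooled contrast and the 9, 18 and 36 mg contrasts are not protected by randomisation against a cohort difference; the 27 mg contrast is. The size rests on two quantities that the documents do not give, D and the fibrate count, and D may be near 0.

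A reader might infer that the primary result is seriously biased, for example from the multipliers at the planned 18 per arm (0.30D pooled, 0.50D single dose). The documents do not support that, since the SAP itself reports low fibrate enrolment. Nor do they support saying that cohort is certainly ignored, because part of the analysis text is redacted. The case for change is that the possible bias is uneven across doses and costs little to remove.

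**What to change.** 1. Compare 9, 18 and 36 mg with main-cohort placebo only, in the MMRM and in the unstratified Wilcoxon and chi-square tests. In the MMRM, either fit the main cohort alone or fit cohort, cohort-by-visit and separate 27 mg groups by cohort. Keep the merged 27 mg contrast as planned.

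2. For the pooled contrast, add cohort and cohort-by-visit to the MMRM, and treat the fibrate cohort as its own stratum in the van Elteren and CMH tests. Cohort-by-visit is needed: in a check with three visits, assumed within-subject correlation 0.3 or 0.6, and D building up in thirds, cohort alone left 0.05D in the pooled contrast at f = 5. If fibrate numbers are too small for this (SAP 7.5.2 already has such a limit for its CMH test, "if the sample size within a stratum is too small (< 5 subjects"), use the main cohort only. Show the main-cohort-only pooled result beside the adjusted one.

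**Cost.** SAP wording and a few tables; no extra data or patients. The single-dose standard error rises from 13.0 or 12.6 to 13.3 (3-6%), and power stays about 87% at 16 against 16. The pooled standard error rises by 1-2% with cohort, or to 10.5 with the main cohort alone (4-11%), where power at 64 against 16 is about 98%. One drawback should be stated in the SAP: the additive cohort term raises the weight of the fibrate-cohort effect in the pooled contrast from 2/74 = 0.03 to 1/15.4 = 0.06 at f = 2, and from 5/77 = 0.06 to 2.5/16.9 = 0.15 at f = 5. That is why the main-cohort-only result belongs beside it.
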